#### **Target lesions**

All measurable lesions up to a maximum of 5 lesions total (and a maximum of two lesions per organ) representative of all involved organs should be identified as target lesions and recorded and measured at baseline. Target lesions will be selected on the basis of their size (lesions with the longest diameter) and their suitability for accurate repeated measurements (either by imaging techniques or clinically). A sum of the longest diameter (LD) for all target lesions will be calculated and reported as the baseline sum LD. The baseline sum LD will be used as reference by which to characterize the objective tumor response.

#### **Non-target lesions**

All other lesions (or sites of disease) including any measurable lesions over and above the 5 target lesions should be identified as non-target lesions and should also be recorded at baseline. It is possible to record multiple non-target lesions involving the same organ as a single item on the case record form (e.g. "multiple enlarged pelvic lymph nodes" or "multiple liver metastases"). Bone lesions may be measurable if  $\geq 1$  cm on MRI. Measurements of these lesions are not required, but the presence or absence of each will be noted throughout follow-up.

#### **Non-measurable disease (PSA)**

All patients will be evaluated for PSA decline. Patients with disease that is not measurable will be eligible for this study and will be assessed for response based on changes in PSA and serial bone scans (if appropriate). Patients who show PSA increases will not be evaluated for PSA progression prior to 12 weeks of study therapy.

**50% PSA Decline:** PSA decline of at least 50% from baseline confirmed by a second measurement at least 3 weeks later. The reference for these declines should be a PSA measured within 2 weeks prior to starting therapy.

**PSA Progression:** Prostate Cancer Working Group 2 (PCWG2) Criteria will be reported. PSA progression occurs when the PSA has increased 25% or greater above nadir and an absolute increase of 2 ng/mL or more from the nadir is documented. Where no decline is observed, PSA progression similarly occurs when a 25% increase from baseline value along with an increase in absolute value of 2 ng/mL or more. Patients will receive a minimum of 12 weeks of therapy prior to being evaluable for this endpoint. PSA progression (without evidence of progression on scans) will not be a criterion for discontinuation of study therapy.

**PSA Response Duration:** The PSA response duration commences on the date of the first 50% decline in PSA. The response duration ends when the PSA value increases by 25% above the nadir, provided that the increase in the absolute-value PSA level is at least 5 ng/mL or back to baseline, whichever is lower.

**Progressive Disease by PSA** (as defined by PSA Progression, above)

**Time to PSA Progression:** The start of the time to PSA progression is the day treatment is initiated. The end date is the time of PSA progression as defined above.

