#### **2.4.2 Secondary Endpoints**

- PSA decline of  $\geq 50\%$  at 12 weeks post therapy initiation
- Time to PSA progression. Defined as a rise in PSA of 50% above nadir value or 25% above baseline if there is no decline.
- Relationship of abiraterone resistance status (primary vs acquired) and outcome
- Time to confirmed development of  $\geq 2$  new bone lesions that cannot be attributable to bone scan flare
- Reduction in pain for symptomatic patients
- Safety
- Serum selinexor levels as a function of dose and time
- Pharmacodynamic analysis of selinexor impact on XPO-1 expression, leukocyte gene expression profile, and macrophage inhibitory cytokine-1 (MIC-1) mRNA expression

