#### **8.4.3 Secondary Analysis (or Analysis of Secondary Endpoints)**

##### PSA decline of $\geq 50\%$ at 12 weeks post therapy initiation

The proportion of patients experiencing a PSA decline from baseline of at least 50% in PSA at 12 weeks following the initiation of study therapy will be presented with a 95% confidence interval.

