##### Time to PSA progression (TTPP).

Time to PSA progression, is defined as the time interval between the date of treatment initiation and the date of either first documented PSA progression, or death due to any cause, whichever comes first. PSA is measured monthly until PSA progression as defined by the PSAWG2 criteria.

Duration of PSA response defined as the time between the first evaluation at which the response criteria are met and the first documentation of PSA progression or death. Early increase in PSA within 12 weeks, when followed by subsequent decline, is ignored in determining this endpoint.

Kaplan-Meier methods will be used to estimate the median time to PSA progression with a 95% confidence interval.

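### PSA progression as written in 7.3 has no confirming value, so fluctuation after week 12 can count as an event; the definition should be unified and confirmation stated

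*Combined protocol and SAP*

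**What the plan says.** All references are to the combined protocol and SAP.

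- **Section 7.3, Non-measurable disease (PSA), PSA Progression:** "PSA progression occurs when the PSA has increased 25% or greater above nadir and an absolute increase of 2 ng/mL or more", measured from nadir. Where there is no decline, the same 25% and 2 ng/mL apply to baseline. No second value is mentioned. The paragraph opens with "Prostate Cancer Working Group 2 (PCWG2) Criteria will be reported".
- **Same section, 50% PSA Decline:** "PSA decline of at least 50% from baseline confirmed by a second measurement at least 3 weeks later".
- **Same section, safeguards:** "Patients will receive a minimum of 12 weeks of therapy prior to being evaluable for this endpoint", and "PSA progression (without evidence of progression on scans) will not be a criterion for discontinuation of study therapy".
- **Sections 2.4.2 and 8.1:** a different threshold, "Defined as a rise in PSA of 50% above nadir value or 25% above baseline if there is no decline". They give no 2 ng/mL condition and no confirmation.
- **Section 8.4.3, time to PSA progression:** the event is the first documented PSA progression or death. PSA is taken monthly until progression by the named working-group criteria, and the median is estimated by Kaplan-Meier with a 95% interval. It adds "Early increase in PSA within 12 weeks, when followed by subsequent decline, is ignored in determining this endpoint".
- **End of PSA response:** 7.3 uses 25% above nadir plus at least 5 ng/mL, or a return to baseline if that is lower. Section 8.4.3 uses PSA progression or death.

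The bone scan rule in 7.3 does contain a confirmation step: new lesions at the first reassessment need a later scan, and progression is dated back to the first one.

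**The concern.** The plan writes confirmation down for a PSA decline and for the first bone scan, but not for a PSA rise. A programmer working from 7.3 would code the first qualifying monthly value from week 12 as the event.

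Two features make an unconfirmed rise prone to false events. The nadir is the lowest of all earlier readings, so it tends to pick out a reading that was low by chance. Each monthly PSA is also a new opportunity to cross the line. The 12-week wait and the early-rise exclusion do not cover transient rises after week 12.

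At stake is a single-arm median with no control arm to share the bias. In patients whose PSA is stable, the group in whom disease control would show, the estimate would partly reflect measurement noise and testing frequency. Under 8.4.3 the same rise also ends PSA response.

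**Working it through.** **The plan's own figure.** There is none for time to PSA progression. The only stated operating characteristics belong to the primary two-stage design in 8.2.1 and do not involve PSA. They reproduce: type I error 0.0477 (stated 0.048), power 90.07% (stated 90.0%) and early stopping 60.85% (stated 60.9%).

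**Inputs from the document.** Rise of 25% and 2 ng/mL; monthly PSA; events counted from week 12 (month 3); reference is nadir, or baseline if there is no decline.

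**Assumptions, not in the document.** Log-normal within-patient error with CV from 5% to 20%. True PSA is flat at 50 ng/mL, or rises from 50 ng/mL with a fixed doubling time. Confirmed means that the next monthly value also meets the rule against the same reference, with the event dated to the first rise.

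**Step 1: the 2 ng/mL floor.** It adds nothing once 0.25 × nadir ≥ 2, that is nadir ≥ 2/0.25 = 8 ng/mL. Below that it helps. With flat PSA of 5 ng/mL and nadir as reference, single-value false progression by month 6 is 0%, 3.5%, 29% and 54% at CV 5%, 10%, 15% and 20%.

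**Step 2: hand check with baseline as reference.** With σ = √ln(1 + CV²), the chance that one reading is at least 1.25 times another from the same flat level is 1 − Φ(ln 1.25 / (σ√2)). At CV 10%, σ = 0.0998, so the argument is 0.2231/0.1411 = 1.58 and the chance is 5.7%. Four looks (months 3, 4, 5 and 6) give an upper bound of 4 × 5.7% = 23%. The looks share one baseline and are correlated, so the simulated 16% is consistent with this. At CV 5% the argument is 3.16, the chance is 0.08%, and four looks give 0.3%, as simulated.

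**Step 3: simulation, flat PSA of 50 ng/mL, false progression by month 6, 25% rule.**

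| CV | Nadir: single → confirmed | Baseline: single → confirmed |
|---|---|---|
| 5% | 1% → 0% | 0% → 0% |
| 7.5% | 20% → 4% | 6% → 1% |
| 10% | 46% → 15% | 16% → 4% |
| 15% | 77% → 41% | 35% → 13% |

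Both reference columns are needed because 7.3 does not say how small a dip counts as a decline. A flat patient with a chance dip could fall under either branch.

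**Step 4: the 50% threshold of 2.4.2 and 8.1, nadir as reference.** The single-value rate by month 6 is about 3% at CV 10% and 27% at CV 15%. Confirmed, it is about 0.2% and 6%. At CV 10%, moving from 25% to 50% (46% to 3%) therefore matters more than adding confirmation to the 25% rule (46% to 15%).

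**Step 5: truly rising PSA, 25% rule, median single → confirmed.**

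- Doubling time 3 or 6 months: month 3 under both rules at every CV.
- Doubling time 12 months: month 4 under both at CV 5% to 10%; month 3 → 4 at CV 15% to 20%.
- Doubling time 24 months: about one month later (for example month 5 → 6 at CV 10%).

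**The case against.** The strongest reply is that the plan names outside criteria in both 7.3 and 8.4.3, and these may supply a confirming value. That stands as far as intent goes. A reader might infer that the sponsor has chosen to declare progression on a single value. The document does not establish this, because it cites the criteria without reproducing them. What remains is that 7.3 spells out an operational rule and ends the time to PSA progression by reference to that rule, with no second value in it. If confirmation is intended, it needs to be written.

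A second reply is that the conflict between 25% and 50% above nadir is the firmer defect. That is right, and the repair has to cover it. It does not remove the point, because the 50% rule has no confirmation either and still gives about 27% false events at CV 15%.

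A third reply is that safeguards exist and entry requires progressive disease, so many patients will have a genuinely rising PSA. This also stands: for fast-rising PSA the median does not move. A reader might infer from the flat-PSA figures that the reported median will certainly be too short. The document does not support that, since it gives neither the PSA variability nor the mix of PSA trajectories.

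Finally, the plan is not strict about decline in its own analysis. Section 8.4.3 reports "The proportion of patients experiencing a PSA decline from baseline of at least 50% in PSA at 12 weeks" without repeating the confirmation in 7.3. This weakens the contrast between the two rules but shows the same need for one definition.

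**Conclusion.** The written rule lacks a confirmation step, and the direction of the resulting bias is clear: an unconfirmed rule can only date events earlier. Its size is conditional. It is near nil at CV 5% or when PSA doubles every 3 to 6 months. It is substantial for flat PSA at CV 10% or more (46% against 15% with nadir as reference, 16% against 4% with baseline). For slowly rising PSA it is about one month on the median. Confirmation reduces false events but does not abolish them: 41% remain at CV 15% with nadir as reference.

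The consequence is confined to descriptive secondary PSA endpoints. PSA progression does not enter rPFS or the two-stage decision rule, and by itself it does not stop therapy. This is a minor-to-moderate point that is cheap to correct. It is not a threat to the trial's main conclusion.

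**What to change.** 1. Use one PSA progression definition in 2.4.2, 7.3, 8.1 and 8.4.3. Reconcile 25% with 50% above nadir, say whether the 2 ng/mL condition applies, and state what counts as a decline when choosing between nadir and baseline. Section 8.4.3 counts death as an event and 7.3 does not; settle that in the same edit.
2. Add for the endpoint: *PSA progression requires a second PSA at least 3 weeks later, normally the next monthly value, that still meets the criterion. The event is dated to the first rise. If no later PSA exists, the single rise counts as the event.*
3. In 8.4.3, have monthly PSA continue to confirmed progression, so that the second value is collected.
4. Reconcile the two rules for the end of PSA response (7.3 and 8.4.3) and confirm that end in the same way.
5. If the cited working-group criteria are meant to supply any of this, write the relevant requirement into the text.

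The cost is wording only. PSA is already drawn monthly, and PSA progression alone does not end therapy, so the second value will normally exist. The downsides are a slightly longer median and reliance on the fallback for a rise at the last visit, since follow-up after the end-of-treatment visit is by telephone. The sample size, the primary analysis and treatment decisions do not change.

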**Abstract**

Title	Phase II Single Agent Study of Selinexor (KPT-330) in Patients with Metastatic Castration-Resistant Prostate Cancer (mCRPC) and Prior Therapy with Abiraterone and/or enzalutamide
Patient population	Patients with abiraterone- or enzalutamide-refractory mCRPC.
Rationale for Study	
Abiraterone acetate is now considered the standard of care for patients with metastatic castrate-resistant prostate cancer (mCRPC) in the pre-chemotherapy setting. Patients with primary or acquired abiraterone resistance typically have rapidly progressive, refractory disease for which limited treatment options are available. The development of new therapies in mCRPC requires a focus on patients with primary or acquired resistance to abiraterone. Patients with abiraterone-refractory mCRPC have a poor prognosis overall with median survival after progression of disease at approximately 19 months. While chemotherapy is a standard approach in this setting, it is refused by many patients and clinicians due to toxicity concerns.
 
Selinexor is a first in class Selective Inhibitor of Nuclear Export (SINE) that specifically blocks the karyopherin protein Exportin 1 (XPO1/Exportin 1). XPO1 is a key regulatory protein responsible for the nuclear export leading to functional inactivation of tumor suppressor proteins (TSPs) and is up-regulated 2-4 fold in all cancers studied to date. Selinexor, given orally, has demonstrated potent anti-cancer activity in animal models of prostate cancer including inhibition of PC3 driven bone metastasis.
 
The goal of this trial is to evaluate the potential for a progression free survival benefit associated with selinexor administration in patients with abiraterone-refractory mCRPC.

Primary Objective	To describe radiographic progression free survival (rPFS) associated with selinexor in patients with abiraterone- and/or enzalutamide-refractory mCRPC

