## 8.4 Analyses Plans

### 8.4.1 Analysis Population

All patients who receive at least 1 dose of selinexor will be evaluated for response.

Only those patients who have measurable disease present at baseline, have received at least one cycle of therapy, and have had their disease re-evaluated will be considered evaluable for response. All analyses will be performed with respect to all patients treated

with selinexor, regardless of prior therapy, with a separate analysis performed according to prior treatment status with cohorts of patients as follows:

- (A) Prior abiraterone only
- (B) Prior enzalutamide only
- (C) Prior concomitant therapy with abiraterone and enzalutamide
- (D) Prior sequenced therapy with abiraterone and enzalutamide

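### Section 7.3 makes patients evaluable for PSA progression only after 12 weeks of therapy, which contradicts 8.4.1 and 8.4.3 and can bias the median time to PSA progression upward

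*Combined protocol and SAP*

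**What the plan says.** Section 7.3, under non-measurable disease (PSA), contains two 12-week sentences. One bars early assessment: "Patients who show PSA increases will not be evaluated for PSA progression prior to 12 weeks of study therapy". The other sets an exposure condition: "Patients will receive a minimum of 12 weeks of therapy prior to being evaluable for this endpoint". The same part fixes the time origin, "The start of the time to PSA progression is the day treatment is initiated", and separates PSA from treatment decisions: "PSA progression (without evidence of progression on scans) will not be a criterion for discontinuation of study therapy". It does not say whether a patient who stops before week 12 is excluded, censored or counted.

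Section 8.4.1 says: "All analyses will be performed with respect to all patients treated" with selinexor.

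Section 8.4.3 ends the interval at "the date of either first documented PSA progression, or death due to any cause, whichever comes first". It has no minimum exposure and plans a Kaplan-Meier median with a 95% confidence interval. After the definition of PSA response duration it adds: "Early increase in PSA within 12 weeks, when followed by subsequent decline, is ignored in determining this endpoint". Because of that position, it is unclear whether the sentence governs time to PSA progression, response duration or both.

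**The concern.** If entry requires 12 weeks of exposure while the clock starts at the first dose, those 12 weeks become guaranteed time. A patient who stops at week 8 for soft-tissue progression, or earlier for clinical deterioration or toxicity, never meets the condition. Nor is the information recovered later. Section 6.1.3 schedules one PSA at the end-of-treatment visit, within 30 days of the last dose, and the follow-up in 6.1.4 is by telephone with no PSA listed.

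The Abstract says that patients with abiraterone resistance "typically have rapidly progressive, refractory disease for which limited treatment options are available", so patients who stop early may well be those whose PSA is also rising. At stake is a named secondary objective. Two analysts following different sections would report different populations, event dates and possibly medians.

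**Working it through.** **1. The passages applied to four patients**

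| Patient | Section 7.3, read literally | Sections 8.4.1 and 8.4.3 |
|---|---|---|
| Qualifying rise at week 4, soft-tissue progression at week 8, stops | Never evaluable | Event at week 4 |
| Qualifying rise at week 4, no decline, stays on | Event at week 12 or later | Event at week 4 |
| Rise at week 4, then decline, stays on | Rise not evaluated | Rise ignored, if the sentence covers this endpoint |
| Dies at week 10 | Never evaluable | Event at week 10 |

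The sections disagree on who is included (rows 1 and 4) and on dating (row 2).

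**2. The plan's own figures**

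The documents give no rate for time to PSA progression. The nearest figures are those of the two-stage design in 8.2.1: 18 then 54 patients, continue with 11 or more progression-free at 16 weeks, reject with 36 or more, rates 0.55 and 0.75.

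- Early stopping: P(X ≤ 10 | n = 18, p = 0.55) = 0.6085 (stated 60.9%).
- Rejection: sum over x ≥ 11 of P(X1 = x) × P(X2 ≥ 36 − x | n = 36) = 0.0477 at p = 0.55 (stated 0.048) and 0.9007 at p = 0.75 (stated 90.0%).

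These reproduce. They concern the primary endpoint and serve below only as a source of rates.

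**3. How many might stop early (assumption)**

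Assume that treatment stops at the design's progression rates with constant hazard. With p the 16-week progression-free rate, the share stopped by week t is 1 − p^(t/16).

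- Week 8, the first scheduled scan: 1 − 0.75^0.5 = 0.134 (7 of 54); 1 − 0.55^0.5 = 0.258 (14 of 54).
- Week 12: 1 − 0.75^0.75 = 0.194 (10 of 54); 1 − 0.55^0.75 = 0.361 (about 20 of 54).

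Scans fall at weeks 8 and 16, so the week-8 figures are closer to what scheduled imaging can trigger before week 12. New bone lesions at week 8 need a further scan at least 6 weeks later (8 + 6 = week 14), which lowers the count. Toxicity and clinical deterioration raise it.

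**4. Effect on the median (simulation)**

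The simulation used 400,000 patients, exponential times, stopping as in step 3, and correlation rho between PSA progression and stopping through a Gaussian copula. PSA time was continuous, although PSA is measured monthly, and deaths were not modelled. Each cell shows the median in weeks for all treated patients with rises counted from the start and censoring at stopping, then the median with patients stopping before week 12 excluded and rises deferred to week 12.

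| True median | 55%, rho 0 | 55%, rho 0.5 | 55%, rho 0.8 | 75%, rho 0 | 75%, rho 0.5 | 75%, rho 0.8 |
|---|---|---|---|---|---|---|
| 8 | 8.0 → 12.0 | 8.9 → 12.0 | 9.0 → 12.7 | 8.0 → 12.0 | 8.4 → 12.0 | 8.3 → 12.0 |
| 12 | 12.0 → 12.0 | 14.1 → 16.6 | 15.0 → 19.7 | 12.0 → 12.0 | 12.9 → 14.4 | 12.9 → 15.6 |
| 16 | 16.0 → 16.0 | 19.8 → 22.7 | 22.7 → 28.2 | 16.0 → 15.9 | 17.7 → 19.4 | 17.8 → 21.1 |
| 20 | 20.0 → 19.9 | 26.0 → 29.2 | 32.5 → 39.1 | 20.0 → 20.0 | 22.7 → 24.5 | 23.5 → 27.1 |

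- The largest shift is 39.1 − 32.5 = 6.6 weeks. With rho = 0 and a true median of 12 weeks or more there is none beyond simulation error.
- In the 8-week row the median rises even at rho = 0, because early rises are deferred.
- Once rises are deferred, censoring the early stoppers instead of excluding them gives the same medians, so relabelling does not help.
- Of patients whose PSA would progress before week 12, 19% to 75% are lost, depending on the scenario. The rest remain and are counted at week 12 or later.
- With rho above 0 even the first number in a cell exceeds the true median (15.0 against 12, for example), because censoring at stopping is itself informative.

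**The case against.** The strongest reply is that the two 12-week sentences say when PSA is judged, not who is analysed. On that reading 8.4.1 and 8.4.3 settle the population and nobody is excluded. The reading is possible, and it rules out treating exclusion as the settled plan. It does not remove the conflict: under 7.3 an early rise without a decline cannot count before week 12, while under 8.4.3 it can. It also leaves early stoppers with no stated handling.

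A reader might infer more than the text supports:

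- **That fast PSA risers drop out.** A PSA rise alone does not end therapy. Such patients leave only if they stop for another reason before week 12; otherwise their event is postponed. Patients with new bone lesions at week 8 may stay on past week 12 awaiting confirmation.
- **That the curve must be flat at 100% to week 12, with a median never below it.** Under 8.4.3 deaths are events, so this is not established.
- **That a true median of 8 weeks reported as 12 shows the effect of exclusion.** That shift comes from deferral, and the 8 weeks is an assumption.
- **That 19% to 36% is an estimate of the patients lost.** It ignores the scan schedule and rests on assumed rates.

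It is also fair that eligibility selects fitter patients: ECOG 0 or 1, life expectancy of at least 12 weeks, and no urgent need for docetaxel. This probably lowers early stopping, but it does not tell the analyst what to do with those who stop.

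**Conclusion.** The concern holds as a contradiction between 7.3 on one side and 8.4.1 and 8.4.3 on the other, with a possible upward bias if 7.3 is followed literally. The bias needs one of two conditions: early stopping associated with PSA progression, or a true median below 12 weeks. With independence and a true median of 12 weeks or more, the median does not change.

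The size cannot be fixed from the documents. Under the stated assumptions inflation is 0 to about 7 weeks relative to an all-treated analysis that counts rises when they occur. Inflation of the reported median is therefore a risk under one reading, not a demonstrated result. The endpoint is a descriptive secondary one in a single-arm study, so the sample size, stopping rules and primary decision rule are untouched. The separate question of how large a PSA rise must be is not part of this point.

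**What to change.** Replace both 12-week sentences in 7.3 and align 8.4.3. Removing only the exposure sentence would leave the bar on early evaluation in place. The text should state that:

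- all treated patients enter time to PSA progression from the first dose;
- a rise before week 12 is disregarded only when a later PSA declines, and this sentence in 8.4.3 applies to time to PSA progression as well as to PSA response duration;
- a qualifying rise with no later decline is an event on the date of that rise, including in a patient who leaves before week 12, using the end-of-treatment PSA in 6.1.3;
- death from any cause remains an event, as in 8.4.3;
- patients with neither are censored at their last PSA.

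If the 12-week deferral is wanted for comparability, report it as a sensitivity analysis. The rule that a PSA rise alone does not stop therapy is unchanged.

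The cost is wording only; the PSA values are already scheduled. The reported median will probably be shorter and less comparable with analyses that defer early rises. Censoring at the last PSA remains informative if patients stop because their disease is worsening, so the report should give the number who stopped before week 12 and why.
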